Study Description:	This is a pilot study evaluating the ability to treat patients with metastatic disease to the spine with same-session MRI-only simulation and treatment with MRI-guided radiotherapy.
Objectives:	Demonstrate that same-session MRI-only simulation and treatment with stereotactic MRI-guided radiotherapy (SMART) for spinal oligometastases is feasible.
Endpoints:	Primary Endpoint(s): Feasibility will be defined as delivery of the first fraction of same-session MRI-only simulation and treatment with SMART in the first on-table attempt for at least 70% of patients. Secondary Endpoints: None
Study Population:	Patients with at least one disease site deemed to be suitable for treatment with spine SBRT as per radiation oncology evaluation.
Phase:	Not applicable.
Description of Sites/Facilities Enrolling:	This is a single center study enrolling at Siteman Cancer Center at Washington University School of Medicine.
Description of Study Intervention:	Consenting and eligible patients will receive MRI-only simulation and stereotactic MRI-guided radiotherapy (2 or 5 fractions).
Study Duration:	48 months for accrual + 4 months of participant duration (screening, treatment, and follow-up) + 12 months for data analysis = 64 months
Participant Duration:	Maximum of 4 months per patient (screening, 2 or 5 fractions of radiotherapy, 3-month follow-up).

1 BACKGROUND

1.1 Spinal Metastases

Despite advances in cancer therapy, metastatic disease is an eventual reality for innumerable oncology patients. With advances in systemic therapies, the life expectancy of cancer patients increases, concomitantly increasing the global burden of metastatic disease (1). As patients live longer with metastases, the role of local therapy to ablate individually symptomatic and threatening tumor foci is increasingly important. Spinal metastases, in particular, are considered critical disease foci for local treatment due to the substantial morbidity and mortality of disease progression in sites proximal to the spinal cord and nerve roots (2).

1.2 Stereotactic Body Radiation Therapy for Metastatic Disease

Within radiation oncology, stereotactic body radiation therapy (SBRT) is a favored modality for local ablation of metastatic disease. SBRT, defined as delivery of high-dose radiation in five or fewer fractions, offers sharp dose gradients that allow physicians to ablate such disease while sparing immediately adjacent critical structures. In-field control rates of metastases treated with SBRT are roughly 80% up to four years after therapy, even in series examining heterogeneous histologies, sites, and dose (3-5). SBRT is particularly favored for oligometastatic disease, a phase in oncogenic progression where malignant clones have not yet achieved widespread malignant potential, often defined as three or fewer progressive sites of disease. Ablation of metastases, particularly oligometastases, may improve not only patient functional status through local control but has also recently been shown to improve overall survival in solid tumor histologies (6-8). Although a majority of patients who undergo SBRT for oligometastatic disease will experience relapse with distant metastases, approximately 20% of patients with in-field control remain disease-free at 2-4 years of follow-up (3, 4, 6). In a randomized prospective study by Palma et al., delivery of SBRT for oligometastases of broad histologic types (five or fewer sites) improved median overall survival from 28 to 41 months compared to palliative standard of care treatments such as chemotherapy (7). Of patients treated with SBRT or other metastectomy who experience recurrence, as many as 60% have very limited metastatic progression that could be amenable to further intervention such as repeated SBRT (8). Epidemiologic data suggests that patients undergoing such repetitive metastectomy have a survival benefit that is comparable to those undergoing their first procedure (9).

Regarding spine metastases in particular, spine SBRT is a proven treatment modality and is often preferred over conventionally fractionated radiation for patients who have good performance status, potentially long projected life spans, and/or radioresistant tumors (10). However, given the proximity of the spinal cord, the clinical standard of care requires magnetic resonance imaging (MRI) or computed tomography (CT) myelography imaging in the process of radiation planning, in order to visualize the spinal cord itself as an organ-at-risk (OAR).

Typically, the spine SBRT treatment-planning paradigm is initiated through a simulation (planning) CT and a simulation MRI (or fusion of previously obtained diagnostic MR

image sets). Simulation typically takes place within several business days of the clinical consult appointment, and an additional 1-2 weeks are needed from the time of simulation before a treatment plan is prepared and verified for delivery. Therefore, a patient may not start treatment until two weeks after their consult appointment. This workflow prolongs patient discomfort from painful osseous and nerve pain and increases the opportunity for further threatening of neurologic functions like ambulation and continence as tumors progress. Ideally, this workflow could be substantially compressed through advances in technology and treatment planning processes.

1.3 Magnetic Resonance Image-guided Radiotherapy

One such advance within radiation oncology is the emergence of magnetic resonance image-guided radiotherapy (MRgRT) over the past five years. MRgRT, which involves RT delivery using an integrated MRI, radiotherapy device, and dedicated treatment planning system, has become a staple at our institution since we became the first to clinically implement it in 2014 (11). Currently, two MRgRT devices are widely used: the original 0.35 Tesla imaging unit integrated with a tri-Cobalt-60 radiotherapy device and the newer device comprising a 0.35T MRI combined with a linear accelerator (MR-linac) (11, 12). Although analyses have demonstrated that complex radiation plans created for the tri-Cobalt-60 source are acceptable (13), plans for small target volumes such as for SBRT are less conformal using a tri-Co-60 device compared to a traditional linear accelerator (14). Until now, this has limited some uses of MRgRT for SBRT, such as for the spine where rapid dose fall-off and conformality adjacent to the spinal cord is critical. However, we have recently completed commissioning of the newer MR-linac device and our institutional analyses indicate that plan quality with the MR-linac is equivalent to CT-based linac plans, like those widely used for spine SBRT (unpublished internal data).

Importantly, these MRgRT devices offer both daily imaging that is sufficient for treatment planning and plan modification “online” (while the patient lies on the treatment table) (15, 16). These daily plans, typically created in response to changes in daily anatomy, are termed “adaptive radiotherapy” (ART). Stereotactic, MRI-guided ART (SMART) has become common at our institution and we have delivered 1060 adaptive treatment fractions in 190 unique treatment courses since 2014 (17, 18). Our primary use of SMART is for abdominal malignancies, for which daily planning while the patient lies on the treatment machine is a useful way to respond to inter-fraction bowel motion (17). However, the SMART treatment planning process could theoretically also be used to generate the original plan, rather than to simply adapt existing plans. For sites like the spine, where treatment is urgent and the anatomy is more predictable, the SMART paradigm might allow creation of spine SBRT plans on the day of treatment, bypassing the need for simulation. Indeed, the SMART treatment planning process already comprises nearly all components of traditional treatment planning, including volumetric imaging, target volume and organ-at-risk delineation by the physician, treatment plan generation, and quality assurance with an independent, Monte Carlo-based dose verification (15, 18).

1.4 Same-Day Radiotherapy Treatment Planning

However, the current treatment planning workflow for SMART has two key characteristics that have precluded same-day original plan generation until this point. One is that SMART is still based on the use of a pre-treatment simulation session, allowing time (1-2 weeks) for careful selection of optimal beam angles and robust planning to target a particular disease site (18, 19). Additionally, the simulation process also includes a CT image that is used to provide geometric information and tissue relative electron densities (and therefore dose) information (13). Ideally, to expedite treatment for spine SBRT, treatment planning could rely on same-day MR imaging alone to create a same-session MR-only simulation and treatment SMART plan-of-the-day.

The first of these obstacles can be sufficiently overcome for same-session MR-only simulation and treatment spine SBRT through simple pre-planning. Spinal anatomy and target volumes are fairly predictable in comparison to other disease sites and follow a pre-determined set of consensus volumes (20). Use of physics pre-planning based upon typical spinal anatomy to create a standard initial set of beam angles could mitigate some of the same-session simulation and on-table planning time requirements. Additionally, spine tumor patients almost uniformly have volumetric diagnostic spine imaging prior to radiation consult, typically with MRI. These image sets can be used in the time between treatment consult and the first treatment day to adjust the standard set of beam angles to individually optimize the tentative pre-plan before the patient is on the treatment table for clinical treatment planning. This use of pre-planning will improve the feasibility of creating the clinical plan in a time frame that is acceptable and tolerable for the patient to be on the treatment table.

Regarding CT-free treatment planning for MRgRT, some progress has been made towards this goal at other institutions, but in a limited setting of very simple radiation treatments that lack the complexity of SBRT. Investigators at the University of Wisconsin have used their MRgRT device for same-session simulation and treatment planning and delivery of the first fraction of 2D and 3D-conformal palliative spine radiation treatments (21). However, following the first treatment fraction, patients then underwent traditional CT simulation and treatment planning; ART was used only to expedite the first fraction. In their treatment planning, bulk density overrides were used to assign electron densities based on typical values for basic tissue types (bone, fat, lung, soft tissue) (21). Bulk density overrides are the only current FDA-approved mechanism for dose extrapolation in MRgRT radiation planning, and can overcome the absence of CT density information (22). Such overrides carry an anticipated dose uncertainty of <3%, which is considered acceptable (23). For reference, the International Commission of Radiation Units and Measurements (ICRU) mandates that dosimetry systems be capable of delivering dose to an accuracy of 5% (24). Other techniques using MR image processing to infer more precise (voxel by voxel) density information are emerging within the field and may be useful in the future for improving the precision of dosimetry in MRI-only planning. However, these techniques are not yet FDA-approved (25). Prospective evaluation of such techniques would be useful to inform further MRI-only treatment planning.

After creating the bulk-density override plans, a second set of 30 corresponding plans were created by reassigning the relative electron density values based on the co-registered CT dataset, and a comparison of plan dosimetric characteristics was made, detailed in Supplementary Table 1. For comparison of PTV coverage, two metrics were used: coverage by 100% of the prescribed dose (35 Gy) and coverage by 95% of the prescribed dose (33.25 Gy). As the dose fall-off for PTV can be steep, these two metrics were used to adequately describe the differences when a small difference in coverage appears as a large difference in dose. The maximum dose to the spinal cord, as well as doses to circumferential volumes expanded 1, 3, 5, 7, and 10 mm outward from the cord, were compared to ensure the geometric robustness of plans calculated with bulk density overrides. Last, when appropriate, the dose received by a small portion of the esophagus (when it was adjacent to the

vertebral body) was compared, as well. The dosimetric differences observed between the plans with bulk density overrides and those recalculated using CT-based relative electron densities, as delineated in Table 1 in the Supplementary Data Section below, are clinically acceptable and were on average within the 5% dose uncertainty recommended by the ICRU.

More specifically, bulk density override MR-only planning is also projected to be safe in terms of dose to the spinal cord, which is the key safety consideration for spine SBRT. The average dose discrepancy for the maximum point was well within the 5% threshold recommended by the ICRU, ranging between 0.2 and 1.8% (Suppl. Table 1). Importantly, these dose discrepancies did not result in spinal cord constraint dose violation in any of the 30 plan comparisons. The projected dose discrepancy identified also met more stringent national guidelines set by the American Association of Physicists in Medicine (AAPM). Per AAPM Task Group (TG) 71, monitor unit (dose) calculations for external photon beam radiation should display 2-3% agreement between an initial calculation method and a second redundant check (26). Similarly, per AAPM TG-142's specific recommendations for stereotactic radiation delivery, the prescribed versus delivered monitor units (dose) discrepancy should be within a 2% threshold (27). Therefore, bulk density override MR-only planning results in a dose projection that not only meets ICRU requirements but also meets more stringent national consensus guidelines in terms of projected dose to the spinal cord. **This indicates that bulk density override MR-only planning is safe for spine SBRT.**

Use of MRI-simulation alone has also been limited by concern over geometric distortions of MR and the complexities of determining of electron density information without CT. These historical obstacles have been all but eliminated by modern advancements. Nyholm et al. found that after standard corrections, uncertainty from MR geometric distortions translated to a maximum error of only 1mm. In fact, by eliminating the need for CT and MRI registration, treatment planning directly on MR images actually reduced spatial uncertainty when compared to CT-based radiotherapy (28). Indeed, based upon our preliminary *in silico* planning analysis above, the any geometric uncertainties present did not meaningfully impact dose projected to serial volumetric expansions of the spinal cord, which is the principle planning concern for safety in SBRT.

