5.1.1 Dose, Fractionation

Radiotherapy will consist of stereotactic body therapy, to be given over either a two or five fraction course, delivered once daily or once every other day for a period of one to two weeks, for a total of two or five treatments (depending on whether a 2 or 5 fraction course is selected). Patients will be planned for an initial prescription dose at the discretion of the treating physician, delivered in two or five total fractions to the PTV, with dose adaptation based on safety constraints that are already approved of to prevent OAR injury. Suggested dose prescriptions are 24 Gy in 2 fractions or 35 Gy in 5 fractions.

[figure not shown]

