5.1.5 SMART Dose Constraints

These shall function as hard constraints in treatment planning, and coverage will be sacrificed to meet these constraints. All listed constraints are for 2 fraction treatment (Table A) or 5 fraction treatment (Table B), which are both acceptable

course fractionations for this study. Adaptive plans will be evaluated under the assumption that the delivered adaptive plan would meet all hard constraints for 2 or 5 fractions with stable anatomy. For example, on a given day, in a 5-fraction course, the maximum cord dose (to 0.5 cc) will be 5 Gy (extrapolate to maximum dose 25 Gy over 5 fractions).

Table A

Organ-at-Risk	Volume	Constraint (Gy)	Other
PRV spinal cord subvolume (thecal sac or 2mm)	<0.03cc	17	-
PRV Cauda Equina	<0.03cc	17	-
Sacral Nerve S1-5	<0.03cc	26	-
Esophagus	<0.03cc	20	-
Pharynx/Larynx	<0.03cc	20	Mean < 9Gy
Brachial Plexus	<0.03cc	21.5	-
Parotid	-	-	Mean < 7Gy
Rectum	<0.03cc	20	-
Trachea	<0.03cc	20	-
Rib	<5cc	45	57
Skin	<10cc	20	-
Stomach	<0.03cc	20	-
Duodenum	<0.03cc	20	-
Small Bowel	<0.03cc	20	-
Large Bowel	<0.03cc	20	-
Kidneys	<0.03cc	26	Mean < 6Gy
Lungs (combined)	-	-	V10Gy < 10% V5Gy < 35%
Liver	-	-	Mean < 8Gy

Table B

Organ-at-Risk	Volume	Max Dose to Volume (Gy)	Max Point Dose* (Gy)
Brainstem (not medulla)	<0.5cc	23	31
Spinal Cord and medulla	<0.35cc	22	28
	<1.2cc	15.6	-
Spinal Cord Sub-volume (5-6mm above and below level treated)	<10% of sub-volume	22	28
Cauda Equina	<5cc	30	31.5
Sacral Plexus	<5cc	30	32
Esophagus	<5cc	19.5	35
Brachial Plexus	<3cc	27	32.5
Heart/Pericardium	<15cc	32	38

Great Vessels	<10cc	47	53
Trachea and Large Bronchi	<5cc	32	40
Rib	<5cc	45	57
Skin	<10cc	36.5	38.5
Stomach	<5cc	26.5	35
Duodenum	<5cc	18.5	26
Small Bowel	<30cc	20	32
Large Bowel	<20cc	28.5	40
Rectum	<35.cc <20cc	50 32.5	55 -
Ureter	-	-	45
Bladder Wall	<15cc	20	38
Penile Bulb	<3cc	30	-
Femoral Heads	<10cc	30	-
Kidneys	mean	18	-
Lungs (combined)	1500cc 1000cc	12.5 13.5	- -
Liver	700cc	21	-

*Max point dose defined as dose to ≤ 0.035 cc.

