APPENDIX A: Supplementary Data

Table 1. Difference in projected dosimetry for MR-only bulk density override planning versus CT-based plans (Calculated as bulk density - CT-based).

PTV1: Vertebral Body						
Metric	Unit	Average	Median	Max	Ave. difference (% of original projected by bulk density plan)	Max difference (% of original projected by bulk density plan)
Difference in PTV coverage by 100% Rx	%	-0.63	-0.64	1.01	-0.7%	1.1%
Difference in PTV coverage by 95% Rx	%	-0.18	-0.21	0.25	-0.2%	0.3%
Difference in spinal cord maximum dose	Gy	0.08	0.11	0.44	0.6%	2.8%
Difference in volume of cord+3mm receiving 28 Gy	cc	0.00	0	0.01		
Difference in volume of cord+5mm receiving 28 Gy	cc	0.00	0	0.05		
Difference in volume of cord+7mm receiving 28 Gy	cc	-0.03	-0.05	0.1		
Difference in volume of cord+10mm receiving 28 Gy	cc	-0.05	-0.05	0.14		
Difference in percent conformity index	%	-2%	-2%	6%		
Difference in percent gradient index	%	-3%	-1%	6%		
Difference in volume of esophagus receiving 19.5 Gy	cc	-0.03	-0.05	0.1		

PTV2: Vertebral Body and Unilateral Pedicle						
Metric	Unit	Average	Median	Max	Ave. difference (% of original projected by bulk density plan)	Max difference (% of original projected by bulk density plan)
Difference in PTV coverage by 100% Rx	%	-1.18	-0.91	3.33	-1.3%	3.7%
Difference in PTV coverage by 95% Rx	%	-0.21	-0.14	0.53	-0.2%	0.5%
Difference in spinal cord maximum dose	Gy	0.15	0.06	0.43	0.7%	1.9%
Difference in volume of cord+3mm receiving 28 Gy	cc	0.00	0	0.03		
Difference in volume of cord+5mm receiving 28 Gy	cc	-0.04	-0.03	0.09		
Difference in volume of cord+7mm receiving 28 Gy	cc	-0.08	-0.06	0.16		
Difference in volume of cord+10mm receiving 28 Gy	cc	-0.10	-0.11	0.15		
Difference in percent conformity index	%	-4%	-2%	11%		
Difference in percent gradient index	%	-3%	-4%	6%		
Difference in volume of esophagus receiving 19.5 Gy	cc	-0.14	-0.03	0.38		

PTV3: Vertebral Body and Bilateral Pedicles						
Metric	Unit	Average	Median	Max	Ave. difference (% of original projected by bulk density plan)	Max difference (% of original projected by bulk density plan)
Difference in PTV coverage by 100% Rx	%	-0.63	-0.48	1.49	-0.7%	1.6%
Difference in PTV coverage by 95% Rx	%	-0.24	-0.18	0.48	-0.3%	0.5%
Difference in spinal cord maximum dose	Gy	-0.05	-0.08	0.26	-0.2%	1.7%
Difference in volume of cord+3mm receiving 28 Gy	cc	0.00	0	0.01		
Difference in volume of cord+5mm receiving 28 Gy	cc	-0.02	-0.02	0.08		

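### The rib row is identical in the 2-fraction and 5-fraction constraint tables, and the general MR-only safety sentence in section 1.4 rests on 35 Gy plans only

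*Combined protocol and SAP*

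**What the plan says.** Section 5.1.1 leaves the prescription to the physician, with guidance: "Suggested dose prescriptions are 24 Gy in 2 fractions or 35 Gy in 5 fractions". Section 5.1.5 gives Table A for 2 fractions and Table B for 5 fractions. It calls both sets hard constraints, to which target coverage must give way. Table A limits the cord on an expanded structure, "PRV spinal cord subvolume (thecal sac or 2mm"), at 17 Gy to <0.03cc. Table B limits the cord and medulla at 28 Gy (point), 22 Gy (<0.35cc) and 15.6 Gy (<1.2cc), and has a further row for a cord sub-volume. The rib row reads <5cc, 45, 57 in both tables.

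The planning evidence is in section 1.4 and Appendix A. Section 1.4 says that "a second set of 30 corresponding plans were created by reassigning the relative electron density values based on the co-registered CT dataset", and that target coverage was compared as "coverage by 100% of the prescribed dose (35 Gy) and coverage by 95% of the prescribed dose (33.25 Gy"). Appendix A has rows such as "Difference in volume of cord+3mm receiving 28 Gy". Section 1.4 reports that "these dose discrepancies did not result in spinal cord constraint dose violation in any of the 30 plan comparisons", cites agreement with professional tolerances, and ends: "This indicates that bulk density override MR-only planning is safe for spine SBRT".

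**The concern.** The tables are separate because the two courses differ in total dose and dose per fraction. A row carried unchanged from one to the other is either an error or a choice that needs explaining. In this workflow the plan is made and checked with the patient on the table, and the hard constraints are what the plan is judged against. If the rib row cannot bind, it gives the planner no working rib limit in a 2-fraction course. The documents do not give the split between 2 and 5 fractions, so anywhere from none to all of the 10 evaluable patients could be affected.

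The second part concerns the stated rationale. Section 1.4 treats cord dose as the main safety question and answers it for spine SBRT as a whole. Anyone relying on that sentence for a 2-fraction patient would be relying on plans made for another prescription, with other dose levels and no tabulated result on the Table A cord structure.

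**Working it through.** **Rib row** (inputs: section 5.1.5, Tables A and B; section 5.1.1)

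- Against the suggested 2-fraction prescription: 45/24 = 1.875, or 188%; 57/24 = 2.375, or 238%.
- Against the suggested 5-fraction prescription: 45/35 = 129%; 57/35 = 163%.
- The next highest dose in Table A is 26 Gy (sacral nerves, kidneys), and 26/24 = 108%. Rib is the only row far above the prescription.
- Only rib and skin have the same volume threshold in both tables. Skin (<10cc) is 36.5 Gy in Table B and 20 Gy in Table A; rib (<5cc) is 45 Gy in both.
- In Table B the third figure is a maximum point dose. Table A has no such column. Its last column, headed Other, otherwise holds only mean-dose and percent-volume limits, so the 57 there is undefined.

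**Regimen covered by the plan comparison** (inputs: section 1.4, Appendix A, section 5.1.5)

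| Level reported | Table B (5 fractions) | Table A (2 fractions) |
|---|---|---|
| Coverage at 35 and 33.25 Gy | Suggested prescription 35 Gy | Suggested prescription 24 Gy |
| Cord expansions at 28 Gy | Cord point limit 28 Gy | Cord PRV limit 17 Gy |
| Esophagus at 19.5 Gy | 19.5 Gy to <5cc | 20 Gy to <0.03cc |

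All three levels belong to the 5-fraction course. Since 28/24 = 117%, a volume receiving 28 Gy says little about a 24 Gy plan. Plan pairs shown: 30 at 35 Gy, none for 2 fractions.

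**The plan's own figures.** The count of no violations in 30 cannot be recomputed, because plan-level doses are not given. The average cord discrepancy is given as "ranging between 0.2 and 1.8% (Suppl. Table 1"). Appendix A lists absolute averages of 0.6, 0.7, 0.2, 1.8, 0.1 and 1.3%, so the low end is 0.1%, a trivial difference. The largest single values are 2.8, 1.9, 1.7, 3.9, 1.9 and 5.6%.

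**How close the plans came to the limit.** Largest Gy difference divided by largest percent difference, assuming both come from the same plan:

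- PTV1 0.44/0.028 = 15.7 Gy; PTV2 0.43/0.019 = 22.6; PTV3 0.26/0.017 = 15.3
- PTV4 0.83/0.039 = 21.3; PTV5 0.30/0.019 = 15.8; PTV6 1.04/0.056 = 18.6

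Headroom to 28 Gy is 28 − 22.6 = 5.4 Gy up to 28 − 15.3 = 12.7 Gy. Scaled by 24/35, the doses are 10.5 to 15.5 Gy, and the smallest headroom to 17 Gy is 17 − 15.5 = 1.5 Gy. The largest error scaled the same way is 1.04 × 24/35 = 0.71 Gy, which is smaller. For a plan that sat at 17 Gy, 5.6% would be 0.95 Gy.

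**The case against.** On the rib row: a limit above the prescription is not in itself a mistake. Table B has several for 35 Gy, such as great vessels at 47 and 53 Gy, and 24 Gy is only a suggestion. Both facts stand. But a 2-fraction prescription would have to reach 45 Gy before the first figure equalled it. The repetition across tables and the misplaced 57 remain unexplained at any prescription.

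On section 1.4: the sentence about violations claims only what was tested. The wider conclusion also rests on percentage agreement with professional tolerances, which are not tied to a fractionation, and density-override errors may carry over roughly in proportion to dose. That is a reasonable argument, but the protocol does not make it, and it would not by itself show that no plan crosses 17 Gy on the Table A structure. Section 1.4 also says that 1 mm and 3 mm cord expansions were compared, which bracket 2 mm. Appendix A, however, tabulates only 3 mm and wider, at 28 Gy.

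A reader might infer that the 30-plan check could not have failed. The figures do not support this. Six ratios do not bound 30 plans. If the Gy and percent maxima come from different plans, each ratio is only a lower bound on cord dose in the plan with the largest Gy error, so the headroom is overstated. Table B's volume limits are not tested by this calculation, and section 1.4 does not name the limit that was checked.

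A reader might also infer that 2-fraction plans would breach the cord limit. On the crude scaling above, 0.71 Gy stays under 1.5 Gy. The Max column appears unsigned (PTV5 esophagus averages −0.29 with a maximum of 0.29), and only an underestimate by the bulk-density plan threatens a limit. For PTV6, the source of the 5.6%, the average (+0.25 Gy) and median (+0.26 Gy) point the other way; for PTV4 the average is −0.36 Gy.

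**Conclusion.** Two limited points stand.

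1. The rib row is the only one with identical figures in Tables A and B. At 188% and 238% of 24 Gy it cannot realistically act as a hard constraint for a 2-fraction plan at the suggested dose. This assumes that such plans do not place 5 cc of rib at nearly twice the prescription. The documents do not show which figures were intended, and this review takes no view on that.

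2. The visible evidence for the safety sentence covers 35 Gy plans at Table B dose levels, while the sentence carries no such limit. That the 5-fraction limits were the ones tested is inferred from the matching levels. The part of section 1.4 that introduces the comparison was not in the text available, and it may hold plan details.

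It does not follow that 2-fraction treatment is unsafe or should wait: Table A still applies to every 2-fraction plan. No endpoint, sample size or analysis changes. The rib row matters more, because it is an operative instruction; the sentence in section 1.4 is background rationale.

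**What to change.** - **Section 5.1.5.** Check the rib rows of Tables A and B against their source and reconcile each with the fractionation its table describes. State what the 57 under Other in Table A means. If the rows are meant to be the same, say so and give the reason.
- **Section 1.4.** Limit the concluding safety sentence to the 35 Gy plans that were compared, and name the cord limit that was checked. Alternatively, keep the general sentence and state the grounds on which it extends to the 2-fraction option in section 5.1.

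The cost is a table check and a wording change, with IRB approval as for any amendment. No patients, visits or procedures are added.
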